- 6) The pregnancy test should be performed within 48 hours of the procedure in women of childbearing ages, using a urine test (or β-HCG) for confirmation.
- 7) Clinical symptoms include abdominal pain, nausea, vomiting, and et al. and will be assessed through inquiries by the investigator.
- 8) The abdominal CT scan for screening should be performed within 6 months of the procedure and the tests conducted at external hospitals are also usable. The abdominal CT scan must be performed to evaluate the clinical success and to ensure the stent removal at Day 30~60 after the procedure.
- 9) The Radiological examination (X-ray) includes the images of abdomen, and the X-ray for screening should be performed within a month of the procedure. Additional photos may be taken if necessary at the discretion of the investigator.
- 10) EUS-guided transluminal drainage will be performed using a SPAXUS stent.
- 11) At Day 30 after the procedure, the stent will be removed using endoscopic forceps or snare according to the standard procedure, if the stent removal criteria are met, at the discretion of the investigator, based on the laboratory test results, clinical symptoms, and abdominal CT scan. However, if the removal criteria are not satisfied at Day 30 after the procedure at the discretion of the investigator, it will be assessed whether the stent can be removed or not at Day 60 after the procedure and the Niti-S SPAXUS™ stent will be removed at the maximum Day 60 after the procedure. If the pancreatic pseudocyst is not resolved at Day 60 after the procedure, the Niti-S SPAXUS™ stent will be removed and a plastic stent will be inserted.
- 12) The clinical success will be assessed by the investigator based on the size of the pancreatic pseudocyst confirmed from the abdominal CT scanning.
- 13) The technical success will be assessed by the investigator based on the position, deployment and fluid status drained of the SPAXUS stent.

§ For the end of treatment (EOT) visit, the visit 5 will be conducted at Day 30 after the procedure and the removal of the stent will be confirmed. If the removal criteria are not met at the discretion of the investigator, visit 5-1 will be conducted at Day 60 after the procedure. At the visit, the investigator will assess the clinical success of the pancreatic pseudocyst and will remove the Niti-S SPAXUS™ Stent.

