## **7. STUDY OBJECTIVE**

This study was planned to confirm the effectiveness and safety of 'Niti-S SPAXUS™ Stent', a lumen-apposing, fully covered, self-expandable metal stent, being used for EUS-guided transluminal drainage for the treatment of pancreatic pseudocyst.

The primary objective is to assess whether the size of the pancreatic pseudocyst is reduced by more than 50% after the intervention to confirm the clinical effectiveness of the Niti-S SPAXUS™ stent.

The secondary objective is to evaluate the incidence and mean of the followings to determine the effectiveness and safety of the Niti-S SPAXUS™ stent.

- Technical success
- Stent lumen patency
- Stent removal success
- Procedure time
- Procedure / Device related serious adverse events
- Other adverse events

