If the subject fails to meet the criteria for stent removal at Day 30 after the procedure, the procedure the investigator will evaluate whether the stent is removable through the laboratory tests, clinical symptoms, and abdominal CT scanning at Day 60 ( $\pm$  10 days) after the procedure. If the drainage is not achieved sufficiently at Day 60 after the procedure and the placement of the drainage tube is required (e.g. untreated pancreatic pseudocysts communicated with the main pancreatic duct), the Niti-S SPAXUSTM stent will be removed and a plastic stent will be inserted. The following procedures will be performed.

- Vital Signs (Blood pressure, Pulse rate, Respiration rate, Body temperature)
- Physical Examination
- Laboratory tests (Hematology, Coagulation, Chemistry)
- Clinical symptoms
- CT Scanning (abdominal CT)
- Removal of Niti-S SPAXUSTM Stent (using endoscopy)
- Evaluation of clinical success
- Evaluation of the stent removal success
- Concomitant Medications /Procedures
- Adverse Events /Serious Adverse Events

< Visit 6>

At Day 20 ( $\pm$  10 days) after removal of the stent, an evaluation of the investigational device and the procedure-related adverse events will be performed and the following procedures will be performed.

- Vital Signs (Blood pressure, Pulse rate, Respiration rate, Body temperature)
- Physical Examination
- Laboratory tests (Hematology, Coagulation, Chemistry)
- Clinical symptoms
- Radiological Examination (X-ray: abdomen)
- Concomitant Medications /Procedures
- Adverse Events /Serious Adverse Events

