### 11.1.2. Effectiveness Assessment Criteria and Methods

- 1) Primary Effectiveness Assessment

- Clinical success

When the size of pancreatic pseudocyst confirmed by abdominal CT at Day 30 or 60 ( $\pm$  10 days) after the procedure of the Niti-S SPAXUSTM stent is reduced by 50% at least compared with the baseline, it will be evaluated as clinically successful.

- 2) Secondary Effectiveness Assessment

- Technical success

If the stent is deployed successfully in the gastrointestinal tract and the pseudocyst, and if the drainage is confirmed visually, it is considered technically successful.

- Stent lumen patency

The stent lumen patency will be evaluated by the investigator at Day 30 or 60 ( $\pm$  10 days) after the procedure of the Niti-S SPAXUSTM stent through clinical symptoms and endoscopy.

- Stent removal success

When the Niti-S SPAXUSTM Stent is successfully removed by using forceps or snare through endoscopy as the treatment is succeeded clinically at Day 30 or 60 ( $\pm$  10 days) according to standard procedures and the criteria for stent removal are met, it is considered as the stent removal success. At Day 30 after the procedure, if the investigator determines that the removal criteria are not met and that a further stent drainage is necessary, the possibility of stent removal at Day 60 ( $\pm$  10 days) after the procedure is evaluated again and the Niti-S

SPAXUS™ Stent will be removed at the time point. However, if sufficient drainage is not achieved even at the maximum of 60 days and a drainage tube (e.g. an untreated pancreatic pseudocyst communicated with the main pancreatic duct) is needed, the Niti-S SPAXUS™ stent will be removed and a plastic stent will be inserted. Plastic stent insertion is not applicable to a clinical success.

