#### Criteria for Stent Removal

The size of the pancreatic pseudocyst is reduced to 3 cm or less based on the maximum cross-sectional area on the CT or the time point of 60 days after stenting

- Procedure time

The time is measured from the moment that the endoscope is inserted into the oral cavity to the time point at which the endoscope is removed.

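### The primary definition of clinical success rests on CT size alone and omits the plan's own rule that a plastic stent is not a clinical success, so such a subject can be coded either way.

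*Combined protocol and SAP*

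**What the plan says.** **Primary definition.** Section 11.1.2 counts a subject as a success when the pseudocyst on CT at Day 30 or 60 "is reduced by 50% at least compared with the baseline, it will be evaluated as clinically successful". It sets no other condition.

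**Other places that define or count success.** Clinical Study Schedule, note 12: "The clinical success will be assessed by the investigator based on the size of the pancreatic pseudocyst confirmed from the abdominal CT scanning". Section 7 states the primary objective as to "assess whether the size of the pancreatic pseudocyst is reduced by more than 50% after the intervention". Section 14.2.2.1 and the synopsis count clinical successes at stent removal. None of these mentions a plastic stent.

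**The contrary sentence.** In section 11.1.2, the paragraph on the secondary endpoint stent removal success ends: "Plastic stent insertion is not applicable to a clinical success". The primary definition does not refer to it, and the protocol does not say which statement prevails.

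**When a plastic stent is placed.** Section 10.3.3 (Visit 5-1): "If the drainage is not achieved sufficiently at Day 60 after the procedure and the placement of the drainage tube is required". Section 11.1.2 says the same in substance. Schedule note 11 is worded differently: "If the pancreatic pseudocyst is not resolved at Day 60 after the procedure".

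**The concern.** The size rule and the plastic-stent sentence ask different questions. The first asks how far the cyst has shrunk. The second asks whether drainage had to continue with another device. If a subject can satisfy the first and still receive a plastic stent, the primary count depends on which line of the protocol the site or programmer follows. A reader who starts from the primary definition, note 12, section 7 or section 14.2.2.1 never meets the sentence.

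The direction of the error is known. Coding on size alone counts subjects who needed replacement drainage as successes, which favours the device. The trial is open-label and single-arm, and the investigator assesses the endpoint, so the choice should not be left until results are visible.

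**Working it through.** **1. Can the overlap occur?**

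| Rule | Where | What decides |
|---|---|---|
| Clinical success | 11.1.2 primary definition; note 12; section 7 | CT size reduction of 50% (at least 50% in 11.1.2, more than 50% in section 7) |
| Plastic stent, drainage-based trigger | 10.3.3 Visit 5-1; 11.1.2 | Insufficient drainage at Day 60 and need for a tube, for example a cyst connected to the main pancreatic duct |
| Plastic stent, resolution-based trigger | Note 11 | Cyst not resolved at Day 60; the term is not defined |

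The drainage-based trigger contains no size threshold. A cyst that has shrunk by half or more may still drain insufficiently and need a tube. That is enough for the two rules to disagree, whatever note 11 means.

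**2. The plan's own sample size.** Inputs from section 9.2: p1 = p0 = 0.96, margin 0.10, one-sided 2.5%, power 80%, withdrawal 10%.

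n = (1.960 + 0.842)² × 0.96 × 0.04 / 0.10² = 30.14, rounded up to 31. Then 31 / 0.90 = 34.4, rounded up to 35. Both of the plan's figures are reproduced.

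**3. What one subject does at the boundary.** The lower limit of the difference from 96% must clear −10%, so the lower limit of the rate must clear 86%. The plan names no interval method. The Wald limit is p − 1.96 × √(p(1 − p)/n).

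- 30/31: 0.9677 − 1.96 × 0.0317 = 0.906, pass.
- 29/31: 0.9355 − 1.96 × 0.0441 = 0.849, fail.

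| n | Method | Last count that passes (lower limit) | One fewer (lower limit) |
|---|---|---|---|
| 31 | Wald | 30 (90.6%) | 29 (84.9%) |
| 31 | Clopper-Pearson | 31 (88.8%) | 30 (83.3%) |
| 35 | Wald | 33 (86.6%) | 32 (82.2%) |
| 35 | Clopper-Pearson | 35 (90.0%) | 34 (85.1%) |

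In every row, recoding one subject at the boundary reverses the conclusion.

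**4. Sensitivity, by assumption only.** The documents give no frequency for the overlap. Suppose the size-only rate is the planned 96% and the plastic-stent rule lowers it by 0, 2, 3 or 5 points. The exact binomial chance of at least 30 successes in 31 (the Wald pass count) is then 65%, 44%, 35% or 22%. The starting value is below the planned 80% because this is an exact binomial calculation and the design formula is a normal approximation. That gap is separate from the present point.

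**The case against.** **The sentence may already settle the matter.** It uses the primary endpoint's own term and stands in the same section, so it can be read as a specific exception: a plastic stent means not a success. Its placement also has a reason, because stent removal success is itself conditional on clinical success. This is probably what the authors meant, and the fix adopts it. It does not remove the point, because the places that define and count the endpoint do not carry the exception. The sentence can also be read as a remark that plastic stenting does not arise among successes, which gives no coding instruction for a subject in whom it does.

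**Note 11 need not create an overlap.** A reader might infer that a cyst reduced by, say, 55% is unresolved under note 11 and so gets a plastic stent. The documents do not establish this. The Visit 5 text in section 10.3.3 describes resolution of the cyst as the primary endpoint, so an unresolved cyst may simply be one that missed the 50% rule. The overlap therefore rests on the drainage-based trigger.

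**The overlap has no size window.** A reader might also infer that every cyst above 6 cm has a range of residual sizes, from 3 cm to half of baseline, in which the rules conflict. That borrows the removal criterion ("The size of the pancreatic pseudocyst is reduced to 3 cm or less", or 60 days reached) as if it triggered a plastic stent. No section says so. The range also treats size as a diameter, while sections 9.1.1 and 11.1.2 refer to the maximum cross-sectional area.

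**One-subject sensitivity is generic.** Any misclassification in a trial of 31 has the same effect at the boundary. That is correct: the calculation shows what a coding choice can do, not how often it will arise.

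**Conclusion.** The point stands as an internal inconsistency in the primary endpoint. Clinical success is defined by CT size in section 11.1.2, note 12 and section 7, while a sentence under a secondary endpoint excludes subjects given a plastic stent. Because the trigger in sections 10.3.3 and 11.1.2 is not a size rule, a subject can fall under both.

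The number of such subjects is unknown and may be zero. The consequence is bounded in direction (size-only coding favours the device) and potentially decisive at the pass boundary, where one subject is enough under either interval method at n = 31 or 35. The Wald figures assume a method that the plan does not name, and the 2, 3 and 5 point reductions are illustrations. It should be corrected before data review. The documents do not support saying that the conflict affects every large cyst, or that the plan's intent is evenly balanced between the two codings.

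**What to change.** Carry the plan's existing sentence into the primary definition in section 11.1.2, and align note 12, section 7 and section 14.2.2.1. Suggested wording: *Clinical success is a reduction of at least 50% in pseudocyst size on CT at the time of stent removal, with no plastic stent inserted at that time. A subject who receives a plastic stent at stent removal counts as a failure.*

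Keep to that. Adding other forms of additional drainage would be a new failure criterion that the plan does not contain.

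The sponsor should also reconcile the two descriptions of when a plastic stent is placed (note 11 against sections 10.3.3 and 11.1.2), so that sites apply and code it the same way. No view is taken here on when one should be placed.

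**Cost.** No new data: concomitant procedures are already recorded at every visit. The observed success rate may be slightly lower than under size-only coding. The edits clarify an endpoint, and section 16.3 lists endpoint changes among the significant amendments that need ministry approval, so a formal protocol amendment is required.

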#### Criteria for Stent Removal

The size of the pancreatic pseudocyst is reduced to 3 cm or less based on the maximum cross-sectional area on the CT or the time point of 60 days after stenting

- Procedure time

The time is measured from the moment that the endoscope is inserted into the oral cavity to the time point at which the endoscope is removed.

## 11.2. Safety Evaluation

### 11.2.1. Safety Evaluation Variables

- Procedural / Device related SAEs
- Other adverse events

### 11.2.2. Safety Assessment Criteria and Methods

- Procedural / Device related SAEs

The incidence of serious adverse events related to the procedure or the Niti-S SPAXUS™ stent is assessed at Day 20 after the stent removal.

- Other adverse events

The severity and incidence of all other adverse events than those mentioned above occurring during the follow-up period are evaluated at Day 20 after removal of the Niti-S SPAXUS™ stent.

Independent member (gastroenterologist) unrelated to the implementation of the clinical study will continue to review the safety data. Advisory member may recommend changes to the clinical investigation plan in order to improve the safety of the study subjects, and may recommend the early termination of the clinical study, if there is a serious risk to the safety of the subjects due to the progress of the clinical study. The data safety monitoring results by independent advisory member will be reported to the IRB at the regular / interim or at the study completion reporting.

## 12. SAFETY ASSESSMENT CRITERIA INCLUDING ADVERSE EVENTS/ ASSESSMENT METHOD AND REPORTING METHOD

### 12.1. Definition of Adverse Event /Adverse Device Event

- ① An "Adverse Event (AE)" refers to any untoward medical occurrence, unintended disease or injury, or untoward clinical signs (including abnormal laboratory findings) in subjects, users or other persons, whether or not related to the investigational medical device
- ② "Adverse Device Event (ADE)" refers to any harmful and unintended event caused by or associated with the investigational medical device, which undeniably has the causal relationship with the investigational device.
- ③ "Unanticipated Adverse Device Effect" refers to any pattern or the risk extent of the adverse device event, which is not consistent in reflection to the medical device related information available such as the description in the investigator's brochure(IB) or the supplementary to the device.

### 12.2. Definition of Serious Adverse Event /Adverse Device Effect

Serious Adverse Event /Adverse Device Effect refers to the adverse events or adverse device effects occurred due to the investigational device, which is applicable to any of the following consequences.

- ① Resulted in death or life threatening
- ② Required inpatient hospitalization or prolongation of existing hospitalization
- ③ Resulted in persistent or significant disability/incapacity
- ④ Caused a congenital anomaly/birth defect

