### 6.3.1. Composition of the Medical Device

The investigational device 'Niti-S SPAXUS™ Stent' is used for drainage of cystic fluid by being connected to the pancreatic pseudocyst through human organs such as stomach or duodenum. It is composed with a stent made of nitinol and introducer system. The stent has a self-expandable structure in which the shape memory alloy wires made of nitinol are woven into a cylindrical mesh. The stent is designed to confirm the position of the stent as coated with a silicone membrane on the surface and insertion of a platinum marker.

The introducer system consists of two shafts. The proximal portion of the inner shaft is made of stainless steel and the distal and outer sheaths are made of thermoplastic material. The median inner diameter of the inner shaft is connected to the distal tip, and a guidewire (Optimos™ Guidewire, TaeWoong Medical Co., Ltd.) is placed through the median inner diameter to pass through the inner lumen. In addition, a blue zone is added to the outer sheath of this product to allow identifying the movement during the stent deployment on the endoscope. A tungsten x-ray marker is inserted into the 1st inner sheath which enables the expansion of the stent can be confirmed through the fluoroscope. The stent was also made of nitinol wires and a platinum marker is inserted to confirm the position of the inserted stent.

[figure not shown]
The following describes the dimensions and names of the Niti-S SPAXUSTM Stent and Introducer system model name.

<Figure 1. Dimensions of the Niti-S SPAXUSTM Stent & Introducer system by Model Name >

Art. No.	Body		Flare	
	Diameter (mm)	Length (mm)	Diameter (mm)	Length (mm)
SS0802FW	8	20	23	6.5
SS1002FW	10	20	25	6.5
SS1602FW	16	20	31	6.5

[figure not shown]
※ Allowable Error: Stent  $\pm 5\%$

[figure not shown]
Art. No.	Outer Diameter (mm)	Usable Length (cm)	Total Length (cm)
SS0802FW	3.3 (10Fr)	180	204
SS1002FW			204
SS1602FW			206

※ Allowable Error: Introducer system  $\pm 10\%$

<Figure 2. Part names of the Niti-S SPAXUS™ Stent & Introducer system>

No.	Part Name	Function
1	Stent Body	Consisted of Nitinol wire
2	Cover membrane	Prevents leakage and facilitates removal with silicone coating
3	Platinum Marker	X-Ray marker that identifies the stent position
4	Connector tube	Prevents Nitinol wire loosening
5	Flare	Prevents stent migration

No.	Part Name	Function
1	Hub	Pass the guidewire through the inner diameter
2	Pusher	Irrigation through the side hole

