#### 2) Preparation of Stent Deployment

- ① Under endoscopic ultrasound guidance, a transluminal puncture is performed using a conventional endoscopic instrument (e.g. a fine-needle aspiration needle) in accordance with the preference of the investigator who operates the intervention, avoiding the blood vessels crossing at the position closest to the target pseudocyst.
- ② Introduce the guidewire (Optimos™ Guidewire, TaeWoong Medical Co., Ltd.) through the lumen of the needle which is used for puncturing into the target pseudocyst sufficiently, and remove the needle while leaving the guidewire in the cyst.
- ③ After removal of the needle, insert an dilating device such as a cystotome (or needle knife) and/or a balloon catheter along the guidewire until it is progressed across the lesion.
- ④ After dilating, carefully remove the dilating device.
- ⑤ Remove the stylet from the distal end of the introducer system.
- ⑥ Ensure that the valve of Y-connector connecting the inner sheath and outer sheath is locked by rotation proximal valve end in a clockwise direction to prevent premature stent deployment.

[figure not shown]

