### **12.3.2. Assessment of the Causal Relationship with the Investigational Medical Device**

A causality for all the adverse events should be assessed by the investigator and properly recorded. Upon the incidence of an adverse event, the investigator shall evaluate the relation with the investigational medical device according to the following criteria.

- ① Definitely related
- ② Probably related
- ③ Possibly related
- ④ Probably not related
- ⑤ Definitely not related
- ⑥ Unknown

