### **12.5. Reporting Method of Adverse Event**

#### **12.5.1. Reporting of Adverse Event**

The investigator is responsible to make assessment of all adverse events occurring during the clinical study period and to record them in the case report forms. All adverse events are to be analyzed in the clinical study report and will be assessed.

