#### **12.5.2. Reporting of Serious Adverse Event · Adverse Medical Device Effect**

Upon the occurrence of any serious adverse event/adverse device effect, the investigator is required to record it in the case report form and the serious adverse event/adverse device effect record form provided by the sponsor, and must report it to the sponsor within 24 hours from the time that the incidence has been known, whether or not related to the investigational device.

The sponsor must notify all unexpected, serious device effects to the investigator, the institutional

review board (IRB) (only applicable when the principal investigator did not report to the IRB or when the reported details require changes) and the Minister of Food and Drug Safety within the time periods specified by each section of the followings.

- 1) Resulted in death or life threatening, the sponsor should report the case within 7 days from the day the fact had been reported or known. However, in such case, the detailed information should be reported additionally within 8 days since the date of initial report.
- 2) In case of all other unexpected serious adverse device effects, the case should be reported within 15 days from the date of report received or getting to know about them.

When there is any additional information regarding the serious adverse events/adverse device effects reported, the sponsor should keep reporting until the adverse device effect is resolved (referring to the disappearance of the adverse device effect or to the impossible follow-up).

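### The safety endpoint counts SAEs related to the procedure or the stent, but the SAE definition (read literally) and the only causality scale refer to the device; separately, the Safety Set depends on eligibility

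*Combined protocol and SAP*

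**What the plan says.** **Endpoint.** Section 11.2.2 evaluates "The incidence of serious adverse events related to the procedure or the Niti-S SPAXUS™ stent" at Day 20 after stent removal. The synopsis (Statistical Method, Safety Evaluation) plans a frequency, a percentage and a 95% confidence interval for it, and Section 14.2.3 again covers procedure-related as well as device-related serious events.

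**Definition of serious.** Section 12.2 covers "the adverse events or adverse device effects occurred due to the investigational device" that meet one of the listed seriousness criteria.

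**Causality.** Under Section 12.3.2, "the investigator shall evaluate the relation with the investigational medical device according to the following criteria". Six categories follow, from definitely related to unknown. No other causality scale appears.

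**Device and procedure.** Section 6.3.1 says of the device: "It is composed with a stent made of nitinol and introducer system". In Section 6.3.2, under preparation of stent deployment, "a transluminal puncture is performed using a conventional endoscopic instrument", and the tract is then dilated with a cystotome or needle knife and/or a balloon catheter.

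**Capture of events.** Section 12.5.1 makes the investigator responsible "to make assessment of all adverse events occurring during the clinical study period and to record them in the case report forms". Section 12.5.2 requires serious events to reach the sponsor within 24 hours, "whether or not related to the investigational device". At Visit 6 (Section 10.3.3), "an evaluation of the investigational device and the procedure-related adverse events will be performed".

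**Safety Set.** The synopsis and Section 14.1 restrict it to consented subjects with an attempted procedure who also met the entry criteria.

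**The concern.** The endpoint is a union: related to the procedure, or related to the device. Deriving it takes two judgements per event, and the protocol gives criteria for only one. The missing one matters most at puncture and dilation, where the instruments are not part of the investigational device. Bleeding and perforation are both listed in Section 12.6.1 as expected during the procedure.

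An investigator applying Section 12.3.2 as written could properly rate a needle-knife bleed as definitely not related to the device. The event belongs in the endpoint, but no stated rule puts it there. Investigators at the six centres could class the same injury differently without any of them breaching the protocol. The literal wording of Section 12.2 adds a second way for the event to drop out.

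The Safety Set is a separate and smaller point: a subject who was treated and may have been harmed can leave both numerator and denominator because of an eligibility finding made afterwards.

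**Working it through.** **1. Tracing one event.** Take a serious bleed caused by the needle knife during dilation.

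- *Is it an adverse event?* Yes. Section 12.1 defines an adverse event regardless of relation to the device.
- *Is it serious in the protocol's sense?* If the due-to-the-device condition in Section 12.2 governs both nouns, no, because the knife is not part of the device. If it governs only device effects, yes. Section 12.5.2 presupposes serious events unrelated to the device, so it conflicts with the literal reading.
- *How is causality rated?* On relation to the device only (Section 12.3.2). An unrelated rating is defensible.
- *Is it in the endpoint?* By the endpoint's wording, yes, since it is related to the procedure. No rating, criterion or derivation rule records that. Visit 6 shows that the assessment was intended but gives no criteria.
- *Which causality categories count as related?* Not stated, including for unknown.

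The gap in the causality scale remains under either reading of Section 12.2.

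**2. Size of the effect.** The documents give no safety sample size and no expected SAE rate. The denominator is the planned enrolment from Section 9.2, which reproduces: (1.960 + 0.842)² × 0.96 × 0.04 / 0.10² = 30.14, rounded up to 31; 31/0.9 = 34.4, rounded up to 35. The event counts below are assumptions. The documents name no interval method, so I used exact (Clopper-Pearson) limits, taken from the beta distribution:

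- lower = B(0.025; x, n − x + 1), set to 0 when x = 0
- upper = B(0.975; x + 1, n − x)

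Effect of leaving out one subject with a procedural SAE, n = 35:

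| All counted | One left out | Fall in upper limit (points) |
|---|---|---|
| 1/35 = 2.9% (0.1 to 14.9) | 0/35 = 0% (0 to 10.0) | 4.9 |
| 3/35 = 8.6% (1.8 to 23.1) | 2/35 = 5.7% (0.7 to 19.2) | 3.9 |
| 5/35 = 14.3% (4.8 to 30.3) | 4/35 = 11.4% (3.2 to 26.7) | 3.6 |

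The change in the rate is always 1/35 = 2.9 points.

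**3. Safety Set.** Start from 3/35 = 8.6% (1.8 to 23.1) and remove one treated subject as ineligible:

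- the subject had the event: 2/34 = 5.9% (0.7 to 19.7)
- the subject did not: 3/34 = 8.8% (1.9 to 23.7)

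The rate can move either way.

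**The case against.** The strongest reply is that nothing is lost and that the intent is clear. Adverse events are defined and recorded whatever their cause, and serious ones go to the sponsor within 24 hours. Section 14.2.3 tabulates and lists serious events, and an independent gastroenterologist reviews the safety data (Section 11.2.2). Puncture and dilation are steps in the device's own instructions for use, so they plainly belong to the procedure, and the endpoint names the procedure wherever it is defined. The phrase in Section 12.2 can be read as qualifying device effects only. The CRF is not among the documents and may already have a field for relation to the procedure. On the Safety Set, subjects are enrolled only after meeting the criteria (Sections 10.3.2 and 10.4), and Section 13.2.2 keeps drop-outs' data in the safety evaluation unless there is a valid reason not to.

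Much of this stands. The event is captured, the milder reading is possible, and a misplaced serious event could well be noticed among about 35 subjects. Exclusion for late-found ineligibility should be uncommon. But none of these provisions supplies a rating of relation to the procedure, and a list of expected events is not an attribution rule. The endpoint should be derivable from the protocol without relying on a CRF that is not shown. Section 13.2.2 concerns drop-outs and does not return an ineligible treated subject to the Safety Set. The percentages do rest on assumed counts and say nothing about how often misclassification would occur.

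**Conclusion.** The concern holds. The procedure half of the endpoint has no causality rating or derivation rule, and Sections 12.2 and 12.5.2 conflict if the first is read literally. A serious puncture or dilation injury may therefore be counted outside the endpoint, although it should still be recorded. The Safety Set wording is a lesser, separate defect.

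One misclassified subject in 35 changes the reported rate by 2.9 points and, for the assumed counts shown, lowers the exact upper limit by 3.6 to 4.9 points. How likely that is cannot be judged from the documents. With no safety hypothesis or threshold, the consequence is confined to the reported estimate and its interval, and no trial decision turns on it. The change should be made, but it is not critical to the validity of the trial.

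**What to change.** - **Section 12.2:** define a serious adverse event by the seriousness criteria alone, whether or not related to the device or the procedure, so that it agrees with Sections 12.1 and 12.5.2.
- **Section 12.3.2 and the CRF:** rate relation to the procedure and relation to the device as two separate items. State which categories count as related, and how unknown is handled.
- **Section 11.2.2, Section 14.2.3 and the synopsis:** derive the endpoint as serious and related to either.
- **Synopsis and Section 14.1:** define the Safety Set as all consented subjects in whom the procedure was attempted, regardless of later eligibility findings.

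The cost is protocol wording and, unless the CRF already has it, one item per adverse event. The sample size does not change. The reported rate of related serious events may come out slightly higher.
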